## **Ethics**

- IRB approval will not need to be sought from another IRB.
- The prospective aspect of this study will include a request for consent while the retrospective aspect will require a waiver of consent. To protect the privacy of participants, charts will only be accessed with a protected password on encrypted computers within a secure network, participants will be unidentifiable, any data stored will be on an encrypted computer, and individual information will solely be used for the purpose of this study.
- No risks to the safety of the patient or parent/guardian are anticipated with participation in this study. There is potential risk associated with the DynaCleft® + Nasal Elevator system, including skin irritation/allergy to the adhesive used in the system. If a skin allergy is encountered, participation in the study will be discontinued and appropriate care given. There is potential risk of breach of confidentiality with participation in this study, though all personal identifiers will be removed. Additionally, there is the risk that participants may tire or lose interest while completing the DynaCleft® + Nasal Elevator protocol.

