### **Retrospective:**

- The control group for this study will be obtained from a retrospective chart review of electronic health records of patients with incomplete cleft lip who underwent surgery without any presurgical interventions. These records will be obtained from the Texas Cleft-Craniofacial Team. Only records of infants with non-syndromic unilateral incomplete cleft lip will be qualified for this study. To eliminate variability, only patients treated by one pediatric plastic surgeon ([name]) will be included. All patients with complete cleft lip, or diagnosed with a syndrome, or had any surgeries not provided by the same plastic surgeon (prior to the initial cheiloplasty) will be excluded. Any records with incomplete data or necessary photographs will also be excluded.

IRB NUMBER: HSC-DB-20-0311

- Necessary photographs are to include those taken at the initial visit soon after birth and those at the visit immediately prior to lip surgery. Photographs need to include those taken in the standard anterior-posterior view, profile view, and worms-eye view.
- Linear measurements will be obtained with a ruler and registered in millimeters. A goniometer will be used to measure angles.

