**Prospective:**

- The study population for the prospective aspect will include recruited newborns with untreated unilateral incomplete cleft lip. Patients whose clefts are associated with a syndrome will be excluded. DynaCleft® + Nasal Elevator therapy will be discussed with parent(s) as a presurgical orthopedic option while awaiting primary cleft lip surgical repair that typically occurs between the ages of 3 to 6 months. Informed consent for participation in the study must be obtained from the patients' parents.
- Study duration will be up to three months of presurgical intervention (similar to the existing nasoalveolar molding NAM appliance protocols).
- Patients will be recruited by the Texas Cleft-Craniofacial team. ○ Infants that match the inclusion criteria will be invited to participate in this study.
- Photographs are to be taken at initial visit prior to presurgical intervention and later at completion of the DynaCleft® therapy immediately prior to lip surgery. Angles to be pictured are to include the standard anterior-posterior, profile, and worms-eye view.
- Linear measurements will be obtained with a ruler and registered in millimeters. A goniometer will be used to measure angles.
- The parents of infants enrolled in the DynaCleft® study will be asked to complete an Infant and New Parent Quality of Life survey at the initial and final visits. Components from this survey were adopted from the Infant and Toddler Quality of Life Questionnaire and the CDC Breastfeeding and Infant Practices Questionnaire (see attachments).

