**Prospective:**

- One evaluator will obtain all photographs to be evaluated in this study, examine Electronic Health Records, and collect necessary data and measurements onto a password protected Microsoft Excel Spreadsheet. Measurements to be recorded may include columellar angles, nostril width, nostril height, width of the lip cleft, etc. While most of the information can be gathered directly from the photographs, some factors may require calculations such as soft tissue ratios if need be. The primary investigator will be blinded to whether or not subject has participated in the DynaCleft® study. Data are to be measured twice and results compared to account for accuracy. Participants are identified on the spreadsheet solely by an assigned code. Factors to be recorded will also include general biographical and physical information (age, gender, weight, etc.), duration of treatment and compliance of caregivers.
- Interaction with

IRB NUMBER: HSC-DB-20-0311

participants in the DynaCleft® study will involve one monthly visit up until date of surgery, usually between 3 to 6 months of age. Each appointment is estimated to be

an hour long to allow for assessment of the orthopedic, recording of information, and addressment of any concerns. The initial and last visits may require more time due to obtainment of necessary photographs. Participants will be required to receive DynaCleft® treatment for at least 2 months before lip surgery to qualify. Additionally, parents of infants with incomplete unilateral cleft lip that choose not to use the DynaCleft® + Nasal Elevator system but are willing to complete the infant quality of life assessment at time of surgery will be allowed to complete the survey. All images obtained in this study will be stored in a password protected and encrypted computer. Prospective patient images will be stored in the Electronic Health Record. Images will be de-identified.

- Parents will be asked to complete the Infant and New Parent Quality of Life questionnaire at both the initial visit and date of surgery.

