### **Data and Safety Monitoring**

- There are no adverse events expected as there is no direct risk involved with the participants. All patient information will be unidentifiable and stored in password protected devices.
- The DynaCleft® + Nasal Elevator system is an FDA approved medical device. Adverse events can include skin irritation from the adhesive tape. In the event of skin irritation, parents will be offered suggestions to limit irritation (including use of duoderm as a barrier between the skin and tape) or will be allowed to terminate their participation in the study.
- Unanticipated problems will be reported to the Center for the Protection of Human Subjects.
- Periodic assessment of research progression and data collection will be reviewed within the pediatric dental department through presentations and research committee meetings. Any deviations from protocol will be addressed with the research committee and appropriate authorities as necessary.

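### Infants who stop the device early can be lost from the four primary endpoints: a new skin allergy ends study participation, and the role of the 2-month treatment minimum is not stated

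*Combined protocol and SAP*

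**What the plan says.** - **Ethics.** On skin allergy: "If a skin allergy is encountered, participation in the study will be discontinued and appropriate care given". The same section expects that some families will flag: "there is the risk that participants may tire or lose interest while completing the DynaCleft® + Nasal Elevator protocol".
- **Data and Safety Monitoring.** For skin irritation, parents are first offered ways to reduce it, including a barrier under the tape, "or will be allowed to terminate their participation in the study". Stopping the device while staying in follow-up is not offered.
- **Study Procedures, Prospective.** "Participants will be required to receive DynaCleft® treatment for at least 2 months before lip surgery to qualify". The text does not say whether this governs enrolment, completion or analysis. Treatment duration and caregiver compliance are recorded.
- **Study Design.** The treated group's second photographs are taken "later at completion of the DynaCleft® therapy immediately prior to lip surgery". The controls' second photographs are "those at the visit immediately prior to lip surgery".
- **Outcome Measures.** All four primary measures are set at the initial examination and at surgery, with no condition about completing therapy.
- **Study Population, Prospective.** Infants with a known allergy to the adhesive are excluded at entry.
- **Statistics.** Ten infants are enrolled and nobody is approached after the tenth. The tests are a paired t-test within patients and a between-group test chosen by distribution. No analysis set, missing-data rule or replacement rule is given.

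**The concern.** Each primary endpoint is a change between two sets of photographs. An infant without the second set contributes neither to the paired test nor to the comparison with controls. If that set is missing because the infant did not tolerate the device, the treated group is selected on something that happened after treatment began, and the controls have no counterpart to that selection. The result would then describe infants who kept using the device. The primary objective is effectiveness in infants with unilateral incomplete cleft lip, and a family deciding whether to start would want the result for all who start. With 10 infants, one or two losses are a large share. A missed pre-surgery photograph cannot be recovered once the lip is repaired.

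**Working it through.** **Step 1. The plan's own figure.** The sample size of 10 rests on feasibility and on similar studies. No effect size, SD, power or early-stop rate is given, so it cannot be reproduced. The point does not depend on it.

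**Step 2. What the rules do to each kind of early stopper.**

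1. *Allergy that appears after entry.* Participation ends, so no later study photograph is due. The infant is lost from all four endpoints. This is a stated rule.
2. *Irritation.* If mitigation works, the infant stays in. If the parents end participation, the infant is lost. An infant who stops the device but remains in the study is not addressed.
3. *Fatigue or loss of interest.* This is foreseen, but no rule says what happens to the data.
4. *Treated for under 2 months.* Exposure is known only after the device is started, so the minimum cannot be an ordinary baseline criterion. There are three readings. As a scheduling rule (present early enough to allow 2 months before surgery), it removes no early stopper. As a filter on the analysis, it removes the infant even if photographed. As a definition of completion, it may remove the infant because the final photographs are placed at the end of therapy.
5. *Stopped after 2 months but before surgery.* The minimum is met, but whether final photographs are taken is not said.

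**Step 3. Size, as illustration only.** The number of early stoppers k, the fraction f of the completers' mean effect that they keep, and the early-stop rate p are all assumptions. All 10 enrolled infants are assumed to start the device, and all k stoppers are assumed to be lost. The all-starters mean is ((10 − k) + k·f)/10 of the completers' mean, so

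overstatement = 10/((10 − k) + k·f) − 1.

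- k = 1: f = 0 gives 10/9 − 1 = 11.1%; f = 0.5 gives 10/9.5 − 1 = 5.3%; f = 1 gives 0%.
- k = 2: f = 0 gives 10/8 − 1 = 25.0%; f = 0.5 gives 10/9 − 1 = 11.1%; f = 1 gives 0%.

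*Precision.* The 95% CI half-width for a paired mean change is t(0.975, n − 1)/√n in SD units: 0.715 at n = 10, 0.769 at n = 9 and 0.836 at n = 8.

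*Chance of at least one early stopper among 10.* 1 − (1 − p)^10 gives 40% at p = 5%, 65% at p = 10% and 89% at p = 20%.

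*No device effect.* The formula above gives no bias when the true effect is zero. Bias can still arise if tolerance is related to the change itself. In a simulation with no device effect and an assumed correlation of 0.3 to 0.8 between tolerance and change, losing the 2 least tolerant of 10 shifts the mean of the rest by 0.097 to 0.255 SD.

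**The case against.** A reader might infer that the four primary endpoints by design cover only infants who tolerated the device. The documents do not support that. Outcome Measures sets the second time point at surgery without requiring completion. The protocol expects taping to continue until surgery, so linking the final photographs to the end of therapy may simply name the usual visit. The 2-month minimum may be a scheduling rule. An infant whose irritation is managed with a barrier stays in. The Study Schedule and Consent Document are listed as attachments but are not visible, and they may cover early stopping. All of this stands, and it limits the point to what the visible rules do.

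A reader might also infer that Statistics contradicts itself over whether 10 counts starters or completers. It does not: 10 are to be enrolled, approaches then stop, and completion by the tenth patient ordinarily means the last enrolled infant finishing.

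Three further arguments carry weight:

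- Known adhesive allergy is excluded at entry, so the allergy rule bites only on new allergies. The Ethics section nevertheless provides for an allergy met during the study.
- Controls are also a complete-case selection, filtered on records and photographs. Their filter is different, however, and does not involve tolerating a device.
- A completer estimate can be a legitimate aim in a 10-infant pilot, and the illustrated shifts are small beside the confidence interval. For a completer effect of 1 SD, one or two stoppers with no benefit shift the mean by 0.1 or 0.2 SD, against a half-width of about 0.72 SD.

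None of this says what happens to an infant who stops early. The allergy rule on its face removes at least some of them.

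**Conclusion.** The point holds in a limited form. One stated rule removes infants with a newly met allergy from the study, and a second, the 2-month minimum, may remove those treated for less. No visible text says that infants who stop early are photographed before surgery or analysed. Under those rules the treated group tends towards infants who kept using the device, while controls face no such condition.

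The size cannot be known from the documents. The 11% and 25% figures assume one or two stoppers of 10 with no benefit; the figure is 0% if stoppers keep the full effect. Analysing all starters would not make families who chose the device comparable with retrospective controls. It would remove one source of selection and show the reader both results. This is a worthwhile, inexpensive improvement and does not invalidate the study.

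**What to change.** - **Ethics.** On skin allergy, stop the device and give care, but keep the infant in follow-up.
- **Data and Safety Monitoring.** Add the option of stopping the device and staying in follow-up. Keep the parents' right to withdraw altogether.
- **Study Design, Prospective.** Take final photographs at the visit immediately before lip surgery for every infant who started the device, unless consent is withdrawn.
- **Study Procedures, Prospective.** Use the 2-month minimum only to define a per-protocol analysis, reported beside an analysis of all who started. State how many stopped early and why.
- **Survey wording (minor alignment).** Study Design (Prospective) says "parents of infants enrolled in the DynaCleft® study will be asked to complete" the survey, and Study Procedures asks for the "questionnaire at both the initial visit and date of surgery". Purpose and the opening of Study Design refer to completers. Align these with the enrolled-parent wording.

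The cost is a short amendment to the protocol and, if its unseen text needs it, the consent document. These infants have lip surgery anyway, and treatment duration and compliance are already recorded. The downside is one pre-surgery study visit for families who stopped, and possibly a less favourable all-starters estimate. Infants whose parents withdraw consent would still be lost.

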## **Data Handling and Record Keeping**

- The source documents will only be accessed with passwords within the University of Texas Health Science Center secure network on an encrypted computer. All data stored will be password protected on an encrypted, password protected computer.
- Human participants will be immediately reassigned to an unidentifiable code and any information collected will be linked solely to this code for confidentiality. Access to any information will be restricted to only the primary evaluator and co-investigators. The recorded data will be destroyed after the completion of the study following the protocols set by the IRB.

## **Quality Control and Assurance**

- There will be a single evaluator collecting any and all data, a single pediatric dentist overseeing the DynaCleft® procedure, and a single plastic surgeon performing all surgical repairs. Evaluator will be blinded to whether or not the participant has had DynaCleft® intervention when reviewing photographs for data collection.
- All data are to be blindly measured and assessed at two separate times to ensure consistency.
- There are no plans to have any third-party monitoring of the collected information.

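### The stated evaluator blinding cannot work as described: the same evaluator obtains the photographs, reads the charts and measures all four primary endpoints

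*Combined protocol and SAP*

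**What the plan says.** Quality Control and Assurance makes two statements side by side. On who does the work: "There will be a single evaluator collecting any and all data". On blinding: "Evaluator will be blinded to whether or not the participant has had DynaCleft® intervention when reviewing photographs for data collection". It also has the data measured blind on two occasions and plans no third-party monitoring.

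Study Procedures (Prospective) lists the tasks: "One evaluator will obtain all photographs to be evaluated in this study, examine Electronic Health Records, and collect necessary data and measurements". The measurements named there are the four primary outcomes: columellar angle, nostril width, nostril height and cleft lip width. The factors recorded also include "duration of treatment and compliance of caregivers". That section blinds a differently named person: "The primary investigator will be blinded to whether or not subject has participated in the DynaCleft® study".

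The safeguards shown are image de-identification ("Images will be de-identified"), participant coding ("Human participants will be immediately reassigned to an unidentifiable code") and a linking log listed under Attachments, whose content is not in the supplied text. Data Handling and Record Keeping gives confidentiality as the purpose of the code. On access it says: "Access to any information will be restricted to only the primary evaluator and co-investigators".

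**The concern.** Each primary endpoint is a hand reading, by ruler or goniometer, from a photograph. The comparison is between a prospective device group and a non-randomised retrospective control group. Blinded reading is the main protection the plan states against a reader who places landmarks a little differently when the group is known. The plan gives the reader tasks that reveal the group, so that protection fails in ordinary use.

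Measuring twice does not replace it. A reader who leans the same way both times is repeatable and still biased. A publication would also claim a safeguard that the procedure did not provide.

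**Working it through.** The main check is a comparison of text. The plan gives no figure on this point to reproduce.

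**Step 1. What the evaluator learns before measuring**

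| Task or access | Where stated | What it reveals |
|---|---|---|
| Obtains all photographs | Study Procedures, Prospective | Control images come from a query of the team's photo database (Study Population, Retrospective). Device-group images are taken at study visits, the last when therapy ends (Study Design, Prospective). Whoever selects an image knows which group it is for. |
| Examines health records | Study Procedures, Prospective | Whether a presurgical device was used |
| Collects all data | Quality Control and Assurance | By implication, treatment duration and caregiver compliance, which arise from device use |
| Access to information | Data Handling and Record Keeping | The primary evaluator has access, with no restriction until measurement is complete |

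**Step 2. Whether any listed safeguard removes that knowledge**

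Codes and de-identification hide identity from outsiders. They do not blind a person who has already obtained the images and read the charts. No section says that someone else codes, crops, masks or reorders the images, or keeps the code link from the reader.

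**Step 3. Who is blinded**

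Study Procedures names the primary investigator; Quality Control and Assurance names the evaluator. The documents do not say whether these are one person. Both sections give data collection to the single evaluator, and neither assigns measurement separately to the primary investigator.

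**Step 4. When a lean would matter**

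Write the change score as surgery reading minus first-visit reading, S − F. A lean b at both visits gives (S + b) − (F + b) = S − F, so it cancels. A lean at the surgery image only gives (S + b) − F = (S − F) + b, which shifts the estimated group difference by b if it occurs in one group only.

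**Step 5. Illustration of size**

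Input from the plan (Statistics): 10 treated infants and a 0.05 threshold. Assumptions: two-sided two-sample t-test (the plan leaves the test open and gives no sidedness), no true effect, 10 or 20 controls (the plan gives no number), and a net lean d in SDs of the change score (the plan gives no SD and no basis for d).

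Noncentrality = d × √(n1·n2/(n1+n2)), with df = n1 + n2 − 2.

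- 10 controls: √(100/20) = 2.236, df 18
- 20 controls: √(200/30) = 2.582, df 28

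For d = 0.5 the noncentralities are 0.5 × 2.236 = 1.118 and 0.5 × 2.582 = 1.291.

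| Net lean d | False-positive rate, 10 controls | False-positive rate, 20 controls |
|---|---|---|
| 0 | 5% | 5% |
| 0.1 | 6% | 6% |
| 0.2 | 7% | 8% |
| 0.3 | 10% | 12% |
| 0.4 | 14% | 17% |
| 0.5 | 19% | 24% |

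These rates are per endpoint. They come from the noncentral t distribution and were recomputed for this note.

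**The case against.** The strongest reply is that the plan leaves masking unspecified rather than impossible. The blinding claim is limited to the time when photographs are reviewed, and codes and de-identified images are provided. The primary investigator is called blinded and is not listed by that title among those with access, so that person might be the intended reader. The dentist overseeing the device is listed separately from the evaluator. Prospective images are stored in the health record and controls are also drawn from health records, so the two image sources are not cleanly separate. The attachments are not shown and might describe a masking step.

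Part of this stands. A step described only in an attachment cannot be excluded, so the conclusion is limited to the procedure as described. The illustration rests on assumed values, is close to nominal at small leans, and should not drive the severity. Infant age will probably reveal the visit whatever is done; this is minor, because a lean cannot depend on group if group is masked.

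The rest does not remove the problem. Blinding at the moment of review cannot be restored to someone who has already sourced the images and read the charts. No section gives measurement to the primary investigator; if that was meant, the text still needs amending. Having another person oversee the device does not blind the evaluator. Wherever images are stored, the person who selects them as control or device images knows the group.

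**Conclusion.** The concern holds. Followed as written, the plan does not have the evaluator blinding it states, and this affects all four primary endpoints. The sections also disagree on which role is blinded. This should be fixed.

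The conclusion rests on the text and not on the calculation. Reader bias is possible, not shown. Only a lean that differs between visits and between groups would bias the comparison. Under the stated assumptions, a net lean of 0.5 SD would raise the false-positive rate per endpoint from 5% to about 19% (10 controls) or 24% (20 controls), while 0.1 to 0.2 SD would raise it only to 6% to 8%.

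**What to change.** Separate image preparation from measurement, using staff already in the plan.

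1. A coordinator or co-investigator who does not measure retrieves the images, extracts chart, duration and compliance data, and holds the linking log.
2. That person gives the reader only coded, cropped, undated images, with both groups and both visits in one random order, and a new random order for the second reading.
3. The reader is someone who neither fits nor follows the device, whether that is the primary investigator or a co-investigator. The reader has no access to charts or the linking log until the measurement file is locked.
4. Amend Study Procedures and Quality Control and Assurance to name the same blinded reader. Amend Data Handling and Record Keeping so that the reader's access begins only after the lock, and add the coordinators to the access list if they handle data.
5. If no such reader is available, remove the statement that measurement is blinded and report this as a limitation.

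The cost is a protocol amendment to three sections, some reallocated tasks and a few hours of image preparation. No extra visits are needed, and no extra staff if a named person not involved with the device can read. One limit remains: tape marks or skin irritation near the lip may still reveal the group in some surgery images.
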